9.4.1 Endpoints and Analyses

Descriptive statistics will be used to summarize the safety, tolerability and activity of NTLA-5001 in treated subjects by cohort within each Arm in dose escalation and for each Arm in safety expansion.

The analysis of safety and tolerability will be a comprehensive evaluation of AEs and/or toxicity, based on occurrence of AEs and DLTs, results of clinical laboratory tests, cytokines, vital signs results, changes in physical examination and need for concomitant medications. Acute tolerability through Week 4 and overall safety profile through Week 112 will be assessed.

Cell kinetics will be assessed via TCR transgene copy number and the proportion of T cells expressing the TCR transgene in PBMC and bone marrow through Week 112 after treatment.

Evaluations will include the following:

- Subject BM will be classified into an AML response group at each assessment according to modified ELN recommendations (Section 13.4). Based on these results, all dosed subjects with AML will be assessed for AML according to [Doehner et al \(2016\)](#) at each postbaseline BM by the investigators. Responder criteria to estimate efficacy in Arm 1 and Arm 2 appear below.
- BM results will be used to determine the following efficacy endpoints:
 - For Arm 1:
 - Rate of objective response, where response is CR without measurable residual disease (CR_{MRD^-}).
 - Duration of response / remission (DOR) for subjects with objective response, from first response until MRD is measured above the lower level of detection for the central laboratory assay, or death from any cause, whichever occurs first.
 - Time to clinical progression, defined as time to BM blast count $\geq 5.0\%$ or time to start of next AML therapy that is needed per investigator's judgment
 - For Arm 2:
 - Rate of objective response, where response is CR_{MRD^-} , CR, complete remission with incomplete hematologic recovery (CRi), morphologic leukemia-free state (MLFS), and partial remission (PR).
 - Rate of composite CR, where composite CR is the sum of CR_{MRD^-} , CR, and CRi.
 - DOR for subjects with composite CR, from first response to progression or death due to any cause, whichever occurs first.
 - Analysis of immune parameters and NTLA-5001 cells

- Overall survival: through Week 112.

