13.4 Appendix 4 Hematological Responses Criteria Definitions

Hematological Response	
CR _{MRD}	Less than or equal to 5% blasts in the bone marrow No evidence of extramedullary disease Full recovery of peripheral blood counts: Platelets > 100,000/ μ l, and ANC > 1,000/ μ l MRD not detected [REDACTED]
CR	Less than or equal to 5% blasts in the bone marrow No evidence of extramedullary disease Full recovery of peripheral blood counts: Platelets > 100,000/ μ l, and ANC > 1,000/ μ l MRD detected [REDACTED]
CRh	Less than or equal to 5% blasts in the bone marrow No evidence of extramedullary disease Partial recovery of peripheral blood counts: Platelets > 50,000/ μ l, and ANC > 500/ μ l
CRi*	Less than or equal to 5% blasts in the bone marrow No evidence of extramedullary disease Incomplete recovery of peripheral blood counts Platelets < 100,000/ μ l or ANC < 1,000/ μ l
MLFS	Less than or equal to 5% blasts in the bone marrow No evidence of extramedullary disease Insufficient recovery of peripheral blood counts: platelets \leq 50,000/ μ l and/or ANC \leq 500/ μ l
Partial Remission (PR)	Bone marrow blasts 6-25% with at least a 50% reduction from baseline
Progressive Disease	An increase from baseline of at least 25% of bone marrow blasts or an absolute increase of at least 5,000 cells/ μ L in the number of circulating leukemia cells
Non-Response	None of the above
Hematological Relapse	Proportion of blasts in bone marrow > 5% or Blasts in peripheral blood after documented CR/CRh/CRi
Extramedullary Disease	
Extramedullary disease	If clinical signs of extramedullary lesions are present, responses are assessed by modified Cheson criteria (Cheson et al, 2007).
Molecular Response	
MRD response	MRD < 0.1% [REDACTED]
MRD complete response	MRD not detected [REDACTED]
MRD relapse	Re-appearance of MRD leukemic cells after MRD complete response

ANC = absolute neutrophil count; CR = complete remission; CRh = complete remission with partial hematologic recovery; CRi = complete remission with incomplete recovery of peripheral blood counts; MLFS = morphologic leukemia-free state; MRD = measurable residual disease; PR = partial remission

* When criteria are met for both CRh and CRi, CRh should be reported. When criteria are met for both CRi and blast-free marrow, CRi should be reported.

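### Does the CRh-over-CRi rule in Appendix 4, which leaves CRi with only MLFS-level counts, call for a change to the response analysis or listing?

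*Protocol*

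**What the plan says.** Protocol Appendix 4 (Section 13.4) gives CR, CRh, CRi and MLFS the same blast and extramedullary conditions. It separates them by platelets and ANC, and splits CR further by MRD. Its footnote has two tie-breaks. The overlap between partial and incomplete recovery is settled by "When criteria are met for both CRh and CRi, CRh should be reported". The lower end of the CRi range has its own rule, which uses a category name found nowhere else in the table: "When criteria are met for both CRi and blast-free marrow, CRi should be reported".

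Blast-free marrow is not a row of the table and is not defined. The hematological relapse row includes "Blasts in peripheral blood after documented CR/CRh/CRi", so it treats CRh as a remission that can be lost.

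Protocol Section 9.4.1 states that "BM results will be used to determine the following efficacy endpoints".

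- **Arm 1:** "Rate of objective response, where response is CR without measurable residual disease".
- **Arm 2 objective response:** CR with or without MRD, plus "complete remission with incomplete hematologic recovery (CRi), morphologic leukemia-free state (MLFS), and partial remission (PR").
- **Arm 2 composite CR:** "Rate of composite CR, where composite CR is the sum of" CR without MRD, CR and CRi.
- **Arm 2 duration of response:** "DOR for subjects with composite CR, from first response to progression or death due to any cause".

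CRh is in neither Arm 2 rate.

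SAP Section 6.2 has investigators assess response by the Appendix 4 criteria and presents recorded status and date in a listing on the Safety Analysis Set. SAP Section 6.5.3 lists all laboratory results. SAP Section 7 removes objective response, composite CR and duration of response, among others, because the sponsor terminated the study with 2 subjects dosed.

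**The concern.** CRh has no upper count limit and CRi has no lower one, so the rows overlap and the footnote decides what is reported. Three things then look wrong.

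1. A CRi entry appears to mean platelets below 100,000/µL or ANC below 1,000/µL. Under the tie-break it can only mean the much lower MLFS range.
2. The better category, CRh, is missing from both Arm 2 rates, while the worse counts labelled CRi are in both. If the planned rates were run, a patient with partial recovery would not be counted and one with insufficient recovery would be.
3. Two orderings are open. CRi is ranked over an undefined term, and CR is not ranked against CRh at all. If CRh outranked CR, even the Arm 1 response rate would be affected.

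A related loose end is that Arm 2 duration of response ends at progression or death, while Appendix 4 has separate rows for progressive disease and hematological relapse.

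**Working it through.** **Inputs** (Protocol Appendix 4; platelets per µL / ANC per µL; blasts at or below 5% and no extramedullary disease held fixed):

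- CR: platelets > 100,000 and ANC > 1,000
- CRh: platelets > 50,000 and ANC > 500
- CRi: platelets < 100,000 or ANC < 1,000
- MLFS: platelets ≤ 50,000 and/or ANC ≤ 500

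The documents give no figure on this point to reproduce, so the check is one of logic.

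**Step 1: what a reported CRi can be.** Not-MLFS means platelets > 50,000 and ANC > 500, which is the CRh count condition. So MLFS = not CRh. A marrow that meets CRi and lies outside the MLFS range also meets CRh and is reported as CRh. Hence (CRi and not CRh) = MLFS. Both identities held at all 121 points of an 11 × 11 grid that included the boundary values:

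| Criteria met | Points |
|---|---|
| CRi and MLFS | 72 |
| CRh and CRi | 33 |
| CRh only | 7 |
| CR and CRh | 9 |
| Total | 121 |

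Every MLFS point (72 of 72) also meets CRi. If blast-free marrow means MLFS, the second tie-break always reports CRi and the MLFS row can never be used. Every CR point (9 of 9) also meets CRh, with no explicit tie-break.

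**Step 2: what this would do to the Arm 2 rates.** The entries below are how many of the 2 rates (objective response, composite CR) each count pattern enters. Reading A: one label, CR ranked first, blast-free marrow means MLFS. Reading B: as A, but MLFS is reported as MLFS. Reading C: any category whose criteria are met counts.

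| Platelets/ANC | Criteria met | A | B | C |
|---|---|---|---|---|
| 120,000/1,200 | CR, CRh | 2 | 2 | 2 |
| 100,000/1,200 | CRh | 0 | 0 | 0 |
| 80,000/800 | CRh, CRi | 0 | 0 | 2 |
| 120,000/800 | CRh, CRi | 0 | 0 | 2 |
| 40,000/1,500 | CRi, MLFS | 2 | 1 | 2 |
| 120,000/400 | CRi, MLFS | 2 | 1 | 2 |
| 30,000/300 | CRi, MLFS | 2 | 1 | 2 |

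The inversion is therefore real on a one-label reading: 80,000/800 scores 0 and 40,000/1,500 scores 2 or 1. If CRh were ranked over CR, the 120,000/1,200 row would fall to 0 on a one-label reading.

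**Step 3: how open the orderings are.** The count rows carry the descriptors full (CR), partial (CRh), incomplete (CRi) and insufficient (MLFS) recovery. Counts of 120,000/1,200 are full recovery, and reporting them as partial would contradict the table's own words. CR over CRh is the sensible reading, and with it Arm 1 response is untouched. For CRi against MLFS an order is given. Only the name is loose, and MLFS is the one row it can plausibly mean.

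**Step 4: what is still analysed.** SAP Section 7 removes both Arm 2 rates, the Arm 1 rate and duration of response. Rates affected: 0. Subjects in the response listing: the 2 who were dosed. The documents do not say which Arm they were in or whether either reached 5% blasts or fewer, so there may be no CRi entry at all. Platelets and neutrophils are required tests (Protocol Appendix 1, Table 13-1) and appear by subject and date in the laboratory listing.

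**The case for a change.** The strongest case for acting is that the logic is exact and the documents disagree with each other. Section 9.4.1 places each marrow in a single response group, which supports the one-label reading and so the inversion. The relapse row counts CRh as a remission, while the response rates do not. The Arm 1 entry description speaks of CR/CRi with no CRh, so a reader of the listing has no cue that a post-infusion CRi is narrower. On duration of response, suppose for illustration a baseline of 40% blasts, remission at 2% and return to 20%: that is relapse, but not a marrow increase from baseline. The disease-response listing is the only such output left, and one explanatory footnote would be cheap.

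The inconsistency stands. The case for the footnote does not. The listing shows what the investigator entered on the CRF. A statement that CRi implies platelets ≤ 50,000 and/or ANC ≤ 500 is true only if the investigator applied the tie-break. Section 9.4.1 and the Arm 1 entry text both use CRi without CRh, so an investigator could have recorded CRi at 80,000/800, and the footnote would then misstate that subject's counts. Making it conditional avoids the error but tells the reader no more than Appendix 4, to which SAP Section 6.2 already refers. The laboratory listing gives the actual values without inference. The duration-of-response question is fair, but that analysis will not be run.

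**Conclusion.** This is a drafting flaw with no consequence in this study. Under the Appendix 4 footnote a reported CRi has exactly the MLFS-level counts, blast-free marrow is undefined, CR against CRh is settled only by the descriptors, and CRh is missing from both Arm 2 rates. These points would matter if the rates were estimated. They are not: 0 rates and 0 duration analyses depend on them, and the remaining exposure is a status column for 2 subjects whose counts are listed separately.

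The conclusion rests on SAP Section 7 standing as written and on the laboratory listing being produced as SAP Section 6.5.3 describes. Anyone reusing these definitions in a study that does estimate response would need to reconcile Appendix 4, its footnote and Section 9.4.1. The documents do not show which choice was intended.

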13.5 Appendix 5 CRS and ICANS Grading

CRS Consensus Grading

CRS Parameter	Grade 1	Grade 2	Grade 3	Grade 4
Fever [*]	Temperature $\geq 38^{\circ}\text{C}$	Temperature $\geq 38^{\circ}\text{C}$	Temperature $\geq 38^{\circ}\text{C}$	Temperature $\geq 38^{\circ}\text{C}$
With Hypotension	None	Not requiring vasopressors	Requiring a vasopressor with or without vasopressin	Requiring multiple vasopressors (excluding vasopressin)
And/or [†] Hypoxia	None	Requiring low-flow nasal cannula [‡] or blow-by	Requiring high-flow nasal cannula [‡] , facemask, nonrebreather mask, or Venturi mask	Requiring positive pressure (eg, CPAP, BiPAP, intubation and mechanical ventilation)

Organ toxicities associated with CRS may be graded according to CTCAE v5.0 but they do not influence CRS grading.

^{*} Fever is defined as temperature $\geq 38^{\circ}\text{C}$ not attributable to any other cause. In patients who have CRS then receive antipyretics or anticytokine therapy such as tocilizumab or steroids, fever is no longer required to grade subsequent CRS severity. In this case, CRS grading is driven by hypotension and/or hypoxia.

[†] CRS grade is determined by the more severe event: hypotension or hypoxia not attributable to any other cause. For example, a patient with temperature of 39.5°C , hypotension requiring 1 vasopressor, and hypoxia requiring low-flow nasal cannula is classified as grade 3 CRS.

[‡] Low-flow nasal cannula is defined as oxygen delivered at ≤ 6 L/minute. Low flow also includes blow-by oxygen delivery, sometimes used in pediatrics. High-flow nasal cannula is defined as oxygen delivered at >6 L/minute.

ICANS Consensus Grading for Adults

Neurotoxicity Domain	Grade 1	Grade 2	Grade 3	Grade 4
ICE score [*]	7-9	3-6	0-2	0 (patient is unarousable and unable to perform ICE)
Depressed level of consciousness [†]	Awakens spontaneously	Awakens to voice	Awakens only to tactile stimulus	Patient is unarousable or requires vigorous or repetitive tactile stimuli to arouse. Stupor or coma
Seizure	N/A	N/A	Any clinical seizure focal or generalized that resolves rapidly or nonconvulsive seizures on EEG that resolve with intervention	Life-threatening prolonged seizure (>5 min); or Repetitive clinical or electrical seizures without return to baseline in between
Motor findings [‡]	N/A	N/A	N/A	Deep focal motor weakness such as hemiparesis or paraparesis
Elevated ICP/cerebral edema	N/A	N/A	Focal/local edema on neuroimaging [§]	Diffuse cerebral edema on neuroimaging; Decerebrate or decorticate posturing; or Cranial nerve VI palsy; or Papilledema; or Cushing's triad

ICANS grade is determined by the most severe event (ICE score, level of consciousness, seizure, motor findings, raised ICP/cerebral edema) not attributable to any other cause; for example, a patient with an ICE score of 3 who has a generalized seizure is classified as grade 3 ICANS.

N/A indicates not applicable.

^{*} A patient with an ICE score of 0 may be classified as grade 3 ICANS if awake with global aphasia, but a patient with an ICE score of 0 may be classified as grade 4 ICANS if unarousable.

[†] Depressed level of consciousness should be attributable to no other cause (eg, no sedating medication).

[‡] Tremors and myoclonus associated with immune effector cell therapies may be graded according to CTCAE v5.0, but they do not influence ICANS grading.

[§] Intracranial hemorrhage with or without associated edema is not considered a neurotoxicity feature and is excluded from ICANS grading. It may be graded according to CTCAE v5.0.

Encephalopathy Assessment Tools for Grading of ICANS

ICE

Orientation: orientation to year, month, city, hospital: 4 points

Naming: ability to name 3 objects (eg, point to clock, pen, button): 3 points

Following commands: ability to follow simple commands (eg, "Show me 2 fingers" or "Close your eyes and stick out your tongue"): 1 point

Writing: ability to write a standard sentence (eg, "Our national bird is the bald eagle"): 1 point

Attention: ability to count backwards from 100 by 10: 1 point

Scoring: 10, no impairment;

7-9, grade 1 ICANS;

3-6, grade 2 ICANS;

0-2, grade 3 ICANS;

0 due to patient unarousable and unable to perform ICE assessment, grade 4 ICANS.

13.6 Appendix 6 Contraceptive Guidance and Collection of Pregnancy Information

13.6.1 Definitions

Women of Childbearing Potential (WOCBP)

Women in the following categories are considered WOCBP (fertile):

1. Following menarche
 2. From the time of menarche until becoming postmenopausal unless permanently sterile (see below)
 - A postmenopausal state is defined as no menses for 12 months without an alternative medical cause.
 - A high follicle-stimulating hormone (FSH) level in the postmenopausal range may be used to confirm a postmenopausal state in women not using hormonal contraception or hormonal replacement therapy (HRT). However, in the absence of 12 months of amenorrhea, confirmation with more than 1 FSH measurement is required.
 - Females on HRT and whose menopausal status is in doubt will be required to use 1 of the nonestrogen hormonal highly effective contraception methods if they wish to continue their HRT during the study. Otherwise, they must discontinue HRT to allow confirmation of postmenopausal status before study enrollment.
 - Permanent sterilization methods (for the purpose of this study) include:
 - Documented hysterectomy
 - Documented bilateral salpingectomy
 - Documented bilateral oophorectomy
 - For individuals with permanent infertility due to an alternate medical cause other than the above, (e.g., Mullerian agenesis, androgen insensitivity, gonadal dysgenesis), investigator discretion should be applied to determining study entry.
- Note:** Documentation can come from the site personnel's review of the participant's medical records, medical examination, or medical history interview.
- If fertility is unclear (e.g., amenorrhea in adolescents or athletes) and a menstrual cycle cannot be confirmed before first dose of study intervention, additional evaluation should be considered.

Contraception Guidance:

CONTRACEPTIVES ^a ALLOWED DURING THE STUDY INCLUDE:
Highly Effective Methods ^b That Have Low User Dependency

• Implantable progestogen-only hormone contraception associated with inhibition of ovulation^c

• Intrauterine device (IUD)

• Intrauterine hormone-releasing system (IUS)^c

• Bilateral tubal occlusion

• Azoospermic partner (vasectomized or due to a medical cause) Azoospermia is a highly effective contraceptive method provided that the partner is the sole sexual partner of the WOCBP and the absence of sperm has been confirmed. If not, an additional highly effective method of contraception should be used. Spermatogenesis cycle is approximately 90 days. Note: documentation of azoospermia for a male participant can come from the site personnel's review of the participant's medical records, medical examination, or medical history interview.
Highly Effective Methods ^b That Are User Dependent

• Combined (estrogen- and progestogen-containing) hormonal contraception associated with inhibition of ovulation^c
○ oral○ intravaginal○ transdermal○ injectable

• Progestogen-only hormone contraception associated with inhibition of ovulation^c
○ oral○ injectable

a) Contraceptive use by men or women should be consistent with local regulations regarding the use of contraceptive methods for those participating in clinical studies.
 
b) Failure rate of < 1% per year when used consistently and correctly. Typical use failure rates differ from those when used consistently and correctly.
 
c) Male condoms must be used in addition to hormonal contraception. If locally required, in accordance with Clinical Trial Facilitation Group (CTFG) guidelines, acceptable contraceptive methods are limited to those which inhibit ovulation as the primary mode of action.
 
d) True abstinence: When this is in line with the preferred and usual lifestyle of the subject.
 
Note: Periodic abstinence (such as calendar, ovulation, symptothermal, post-ovulation methods), withdrawal (coitus interruptus), spermicides only, and lactational amenorrhea method (LAM) are not acceptable methods of contraception for this study. Male condom and female condom should not be used together (due to risk of failure from friction).

13.6.2 Collection of Pregnancy Information

Male Subjects with Partners Who Become Pregnant

The investigator will attempt to collect pregnancy information on any male subject's female partner who becomes pregnant while the male subject is in this study.

After obtaining the necessary signed informed consent from the pregnant female partner directly, the investigator will record pregnancy information on the appropriate form and submit it to the

Sponsor within 24 hours of learning of the partner's pregnancy. The female partner will also be followed to determine the outcome of the pregnancy. Information on the status of the mother and child will be forwarded to the Sponsor. Generally, the follow-up will be up to 2 years following the estimated delivery date. Any termination of the pregnancy will be reported regardless of fetal status (presence or absence of anomalies) or indication for the procedure.

Female Subjects Who Become Pregnant

The investigator will collect pregnancy information on any female subject who becomes pregnant while participating in this study. Information will be recorded on the appropriate form and submitted to the Sponsor within 24 hours of learning of a subject's pregnancy.

The subject will be followed to determine the outcome of the pregnancy. The investigator will collect follow-up information on the subject and the neonate, and the information will be forwarded to the Sponsor. Generally, follow-up will be 2 years postdelivery. Any termination of pregnancy will be reported, regardless of fetal status (presence or absence of anomalies) or indication for the procedure.

A spontaneous abortion (occurring at < 22 weeks gestational age) or still birth (occurring at ≥ 22 weeks gestational age) is always considered to be an SAE and will be reported as such.

Any poststudy pregnancy-related SAE considered reasonably related to the study treatment by the investigator will be reported to the Sponsor as described in Section 8.5.7.

13.7 Appendix 7 Coronavirus Disease 2019 (COVID-19) Guidance

- Subjects who test positive for coronavirus disease 2019 (COVID-19) using a test consistent with the institutional standard of care or who are exhibiting symptoms consistent with COVID-19 should not be enrolled in the study until complete resolution of symptoms and 2 subsequent negative results for COVID-19 with an approved PCR-based test.
- If the ICF cannot be signed or collected in person due to COVID-19 restriction, alternative approaches of obtaining and documenting informed consent may be utilized in according with local regulatory guidance.
- If an enrolled subject is exhibiting symptoms consistent with COVID-19, contact the Medical Monitor within 1 business day to ensure appropriate documentation and management of study activities.
- If a subject is unable to travel to the site for protocol-specified study visits and procedures, he/she can remain in the trial, provided that safety monitoring can occur. Alternatives, such as telemedicine to conduct visits, should be considered.
- On-site monitoring visits may be replaced by remote monitoring visits during COVID-19. Additionally, remote source document verification may be utilized for critical data points.
- Additional COVID-19 guidance from Food and Drug Administration (FDA), European Medicines Agency (EMA), and Medicines and Healthcare Products Regulatory Agency (MHRA) should be followed in consultation with medical monitor.
- A risk assessment indicates interaction between the administration of NTLA-5001 and COVID-19, seasonal influenza, and pneumococcal vaccines are unexpected. The immunizing effects of COVID-19, seasonal influenza, and pneumococcal vaccinations may be reduced in subjects if the vaccination is administered during periods of immunosuppression. Immunosuppression could occur in subjects due to the effects of AML on bone marrow function and/or during the time from lymphodepleting chemotherapy until bone marrow recovery from its effects. Lymphodepletion may also reduce the established immune protection from any infectious agents including COVID-19. Thus, the timing of COVID-19 vaccination for subjects entering study should be planned by the treating physician with these considerations in mind.

